## **Investigator Documentation Responsibilities**

All individual, subject-specific study data will also be entered into a 21 CFR Part A1-compliant electronic data capture (EDC) system on an eCRF in a timely fashion.

All data generated from external sources (eg, laboratory and bioanalytical data), and transmitted to PPD electronically, will be integrated with the subject's eCRF data in accordance with the Data Management Plan.

An eCRF must be completed for each subject who signs an ICF and undergoes any screening procedures, according to the eCRF completion instructions. The Sponsor, or CRO, will review the supporting source documentation against the data entered into the eCRFs to verify the accuracy of the electronic data. The Investigator will ensure that corrections are made to the eCRFs and that data queries are resolved in a timely fashion by the study staff.

The Investigator will sign and date the eCRF via the EDC system's electronic signature procedure. These signatures will indicate that the Investigator reviewed and approved the data on the eCRF, data queries, and site notifications.

# Publications

If on completion of the study the data warrant publication, the Investigator may publish the results in recognized (referred) scientific journals subject to the provisions of the clinical study agreement (CSA). Unless otherwise specified in the Master Services Agreement, the following process shall occur:

If the Investigator expects to participate in the publication of data generated from this site, the institution and Investigator shall submit reports, abstracts, manuscripts, and/or other presentation materials to the Sponsor for review before submission for publication or presentation. The Sponsor shall have 60 days to respond with any requested revisions, including without limitation, the deletion of confidential information. The Investigator shall act in good faith upon requested revisions, except the Investigator shall delete any confidential information from such proposed publications. The Investigator shall delay submission of such publication or presentation materials for up to an additional 90 days in order to have a patent application(s) filed.

Appendix 5: Schedule of Assessments

# Table 3:Schedule of Assessments

	Screening (Day -28 to Day -2)		Treatment Period			Follow-up Visit
		Check-in (Day -1)	Day 1	Day 2	Discharge (Day 3)	Day 8 to Day 11 (7 to 10 days postdose)
Informed consent	Х					
Demographic data	Х					
Inclusion/exclusion criteria	Х	Х				
Medical history	Х	$X^{a}$				Х
Serology	Х					
Urine drugs of abuse screen (including cotinine)	х	Х				
Alcohol breath or urine test	Х	Х				
Pregnancy test	Х	Х				Х
Study residency						
Check-in		Х				
Discharge					Х	
Nonresidential visit	Х					Х
Dosing with L606 or placebo			Х			
Inhalation administration training b		Х				
Safety and tolerability						
Adverse events c	Х	Х	Х	Х	Х	Х
Concomitant medication	Х	Х	Х	Х	Х	Х
Physical examination d	Х	Х			Х	Х
Body weight, height, and BMI e	Х	Х				
Safety 12-lead ECG f	Х	Х	Х	Х	Х	Х
12-Lead Holter monitor recording g		Х	Х	Х		
Vital signs h	Х	Х	Х	Х	X	Х
Oxygen saturation i		Х		Х	Х	Х
Spirometry j	Х	Х		Х	Х	Х
Clinical laboratory evaluations k	Х	Х		Х	Х	Х
PT, aPTT, INR	Х					
Methemoglobin 	X			Х		
Pharmacokinetics						
Blood sampling for PK analysis of treprostinil m			Х	Х		

Protocol

Abbreviations: AE = adverse event; aPTT = activated partial thromboplastin time; BMI = body mass index; ECG = electrocardiogram; ICF = Informed Consent Form; INR = international normalized ratio; PK = pharmacokinetic; PT = prothrombin time; SAE = serious adverse event.

- a Updated medical history (from Screening).
- b All doses will be self-administered under the supervision of a trained professional in the CRU. Administration instructions and training will be provided and included in separate documents.
- c Between the time of signing the ICF and drug administration, only SAEs will be recorded. All AEs (serious and nonserious) will be recorded as of the time of dose administration until final discharge from the study.
- d Full physical examination at Screening and symptom-directed physical examinations at Check-in, Discharge, and Follow-up.
- e Weight is measured at Screening and Check-in. Height and BMI is measured only at Screening.
- f Twelve-lead safety ECGs will be collected at Screening; Check-in; Day 1 predose, 4, and 24 hours postdose; Discharge; and Follow-up. Subjects will be required to rest in a supine position for at least 5 minutes prior to the ECG extraction timepoints. Assessment times postdose are relative to the end of the inhalation treatment.
- g Electrocardiogram parameters will be measured using a 24-hour continuous 12-lead Holter monitor beginning the night of Day -1 in order to obtain 8 to 12 hours of predose baseline data, and through 24 hours postdose.
- h Supine blood pressure, supine pulse rate, and respiratory rate will be taken at Screening; Check-in; Day 1 predose and at 0.25, 30, 1, 1.5, 2, 4, 8, 12, and 24 hours postdose; Discharge; and Follow-up. Oral body temperature will be taken at Screening; Check-in; Day 1 predose; Discharge; and Follow-up. Orthostatic vital signs will be assessed at Check-in; Day 1 predose; and at 1, 4, and 8 hours postdose. Assessment times postdose are relative to the end of the inhalation treatment.
- i Oxygen saturation will be measured at rest by standard pulse oximetry Check-in, Day 2, and Discharge.
- j Spirometry (forced expiratory volume in 1 second and forced vital capacity) will be measured in a sitting position, if possible, at Screening, Check-in, Day 2, Discharge, and Follow-up. Pre- and post-bronchodilator spirometry testing will be completed at Screening using albuterol; all other timepoints will not require post-bronchodilator testing.
- k Clinical laboratory evaluations including clinical chemistry, hematology, and urinalysis.
-  Methemoglobin will be measured noninvasively using a finger probe.
- m Blood sampling for PK analysis of treprostinil at Day 1 predose and at 0.25, 0.5, 1, 1.5, 2, 4, 6, 8, 10, 12, 14, 16, and 24 hours postdose. Sampling times postdose are relative to the end of the inhalation treatment.

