#### Study design:

This will be a Phase 1, single-dose, randomized, double-blind, placebo-controlled, sequential-group study conducted at a single center.

Potential subjects will be screened (Days -28 to -2) to confirm that they fulfil the eligibility inclusion/exclusion criteria to enter the study. After verification of eligibility, subjects will be admitted to the Clinical Research Unit (CRU) on Day -1 (Check-in, the day before dosing). On Day 1, prior to dose administration, subjects will be randomized in a double-blinded fashion to L606 or placebo in a 6:2 randomization ratio.

The planned emitted dose escalation groups are:

- Group 1: 51 µg L606 or placebo volume equivalent to 51 µg
- Group 2: 102 µg L606 or placebo volume equivalent to 102 µg
- Group 3: 153 µg L606 or placebo volume equivalent to 153 µg
- Group 4: 204 µg L606 or placebo volume equivalent to 204 µg
- Group 5: 255 µg L606 or placebo volume equivalent to 255 µg
- Group 6: 306 µg L606 or placebo volume equivalent to 306 µg
- Group 7: 357 µg L606 or placebo volume equivalent to 357 µg
- Group 8: 408 µg L606 or placebo volume equivalent to 408 µg

L606 or placebo will be administered once in a solution for inhalation. The entire treatment procedure will be completed within 10 minutes.

On Day 3 (48 hours postdose), subjects will be discharged from the CRU after all protocol-specified assessments have been completed. Subjects will return for a Follow-up visit 7 to 10 days postdose. Based on the ongoing review of the safety, tolerability, and PK results, additional nonresidential visits may be required.

Safety and PK data will be reviewed following the completion of each group. Based on this data (as well as aggregate data from previous groups), a decision will be made to proceed with:

- 1) escalation to the next higher planned dose;
- 2) repeat evaluation of the same dose in an additional group;
- 3) evaluation of a lower intermediate dose before moving on to the next higher dose; or
- 4) discontinuation of dosing.

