#### 2.2. Endpoints

#### 2.2.1. **Primary Endpoints**

The primary safety endpoints for this study are as follows:

- incidence and severity of AEs
- incidence of serious AEs (SAEs)
- vital sign assessments (supine blood pressure, supine pulse rate, and respiratory rate)
- 12-lead electrocardiogram (ECG) parameters
- incidence of laboratory abnormalities, based on hematology, clinical chemistry, and urinalysis test results
- physical examinations.

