## 3.7. Dose Escalation Stopping/Dosing Stopping Criteria

If any of the following scenarios occur within a group, dose escalation will be stopped, dose levels will not be repeated, and higher dose levels will not be tested:

• Clinically relevant signs or severe symptoms of similar nature occur in ≥2 subjects within a group, which in the opinion of the safety review team warrant stopping of dose escalation.

- A symptomatic drop in blood pressure from supine to standing of >20 mmHg systolic and/or >10 mmHg diastolic is seen in ≥2 subjects within a group.
- Occurrence of any SAE, which in the opinion of the Principal Investigator, is deemed to be related to study drug.
- Evidence of clinically significant increases in liver function tests (aspartate aminotransferase [AST], alanine aminotransferase [ALT], bilirubin, and gamma glutamyl transferase, defined as ALT or AST >5 × the upper limit of normal [ULN]; or ALT or AST >3 × ULN with a total bilirubin of >2 × ULN with symptoms [ie, monitor for drug-induced liver injury] compared with Day -1) in ≥2 subjects within a group (confirmed with repeat testing).
- Moderate nausea or vomiting that prevents a subject from eating a meal on 3 or more occasions on 2 successive days in ≥2 subjects within a group.
- Symptomatic decrease in supine systolic or diastolic blood pressure of ≥30 or ≥20 mmHg, respectively, from predose baseline in ≥2 subjects within a group.
- Symptomatic decrease in orthostatic systolic or diastolic blood pressure of ≥30 or ≥20 mmHg, respectively, from supine value in ≥2 subjects within a group.
- Forced expiratory volume in 1 second (FEV1) or forced vital capacity (FVC) <65% of predose baseline in ≥2 subjects within a group.
- Symptomatic bronchospasm requiring therapy in  $\geq 2$  subjects within a group.
- Incapacitating dyspnea or coughing, hypoxemia (oxygen saturation ≤90%) in ≥2 subjects within a group.
- Methemoglobin  $\geq 7\%$  in  $\geq 2$  subjects within a group.

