### 7.2.3. Vital Signs

Supine blood pressure, supine pulse rate, respiratory rate, and oral body temperature will be assessed at the times indicated in the Schedule of Assessments in Appendix 5. Vital signs may also be performed at other times if judged to be clinically appropriate or if the ongoing review of the data suggests a more detailed assessment of vital signs is required.

Day 1 predose blood pressure, pulse rate, and respiratory rate will be measured in triplicate at approximately 2-minute intervals. The median value will be used as the baseline value in the data analysis. All subsequent measurements will be performed singly. Oral body temperature will be measured singly.

Subjects must be supine for at least 5 minutes before blood pressure and pulse rate measurements.

For orthostatic vital sign measurements, the supine blood pressure and pulse rate will be measured after the subject has been supine for at least 5 minutes. The subject will then stand for at least 2 minutes and the standing blood pressure and pulse rate will be measured.

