## 7.2.5. Continuous 12-Lead Holter Monitoring

Electrocardiogram parameters will be measured using a 24-hour continuous 12-lead Holter monitor beginning the night of Day -1 in order to obtain 8 to 12 hours of predose baseline data, and through 24 hours postdose.

Subjects will be connected to a Holter ECG recording device and the ECG recording will be started. Subjects will be instructed to avoid strenuous physical exercise or any other activity that could interfere with the quality of the Holter ECG recording or lead to detachment of ECG skin electrodes during the continuous Holter recording period.

During the Holter recording period, the Holter leads should be checked prior to each scheduled PK blood collection. Subjects should be instructed to inform appropriate study site personnel immediately upon discovery of a device or lead failure. Any failures of the Holter device or accessory hardware (electrodes, leads, batteries, etc.) will be recorded in the source documents.

All data will be sent for central ECG evaluation. A data file containing central ECG evaluation will be provided for inclusion in study analysis. Any Holter ECG reports provided to the site will be archived as source documentation only. Holter ECG start and end times should be recorded on the CRF.

Details of the Holter ECG recording will be provided in the ECG manual provided by the central reader.

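### The only list of supine vital-sign times has 30 hours where 0.5 hours is evidently meant

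*Protocol*

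**What the plan says.** Section 2.2.1 of the Protocol names, among the primary safety endpoints, "vital sign assessments (supine blood pressure, supine pulse rate, and respiratory rate"). Section 7.2.3 states no postdose times for them; it says only that they "will be assessed at the times indicated in the Schedule of Assessments in Appendix 5". The grid of Table 3 in Appendix 5 marks vital signs by day, so the clock times stand only in footnote h: "Day 1 predose and at 0.25, 30, 1, 1.5, 2, 4, 8, 12, and 24 hours postdose".

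Three other places bear on how that entry should be read:

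- The second series in footnote h: "Orthostatic vital signs will be assessed at Check-in; Day 1 predose; and at 1, 4, and 8 hours postdose".
- The PK times in footnote m of the same table: "Day 1 predose and at 0.25, 0.5, 1, 1.5, 2, 4, 6, 8, 10, 12, 14, 16, and 24 hours postdose".
- The length of stay, in the Synopsis: "On Day 3 (48 hours postdose), subjects will be discharged from the CRU".

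Section 3.7 makes supine pressure part of a rule for ending escalation: "Symptomatic decrease in supine systolic or diastolic blood pressure of ≥30 or ≥20 mmHg, respectively, from predose baseline in ≥2 subjects within a group".

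**The concern.** An entry of 30 in a list whose unit is hours means 30 hours. That puts the second postdose reading after the last one in the list (24 hours) and leaves no supine reading scheduled between 15 minutes and 1 hour.

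The interval matters. This is the first human study of L606, and Section 1.2.1 describes treprostinil as a strong vasodilator. Section 1.2.4 reports that inhaled treprostinil peaks at a mean of 0.15 to 0.20 hours. L606 is designed to release the drug more slowly, and Section 3.4.1 accepts that its safety profile cannot be fully inferred from the other formulations. From Cohort 3 upward the planned respirable dose (91.8 µg or more, Table 2) exceeds the maximum tolerated respirable dose given there for Tyvaso (67.2 µg). A routine blood pressure at half an hour is therefore a useful part of the safety data.

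A literal reading is also workable in practice. Subjects are still resident at 30 hours, and the grid of Table 3 already carries a vital-signs mark on Day 2. Someone building the case report form or a site worksheet would find nothing in the grid that conflicts with a 30-hour entry.

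**Working it through.** The protocol states no statistical figure on this point. The check compares the two lists and works out the intervals.

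**1. The lists side by side (hours postdose)**

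| Position | Supine vital signs, footnote h | PK samples, footnote m |
|---|---|---|
| 1 | 0.25 | 0.25 |
| 2 | **30** | **0.5** |
| 3 | 1 | 1 |
| 4 | 1.5 | 1.5 |
| 5 | 2 | 2 |
| later | 4, 8, 12, 24 | 4, 6, 8, 10, 12, 14, 16, 24 |

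Footnote h has nine postdose times. Eight of them (0.25, 1, 1.5, 2, 4, 8, 12, 24) also appear in footnote m; 30 is the only one that does not. It is also the only entry that breaks the ascending order.

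**2. The likely intended value**

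30 minutes / 60 = 0.5 hours. With 0.5 in position 2, the list ascends strictly and all nine times coincide with PK samples. A lost decimal point is a weaker explanation: 0.30 hours is 0.30 × 60 = 18 minutes, only 3 minutes after the 15-minute reading, and 3.0 hours would still be out of order.

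**3. What a literal reading does**

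- Readings within 24 hours: 8 of 9. The ninth, at 30 hours, falls 30 − 24 = 6 hours after the 24-hour reading and 48 − 30 = 18 hours before discharge.
- Gap in the first hour as written: 1 − 0.25 = 0.75 hours = 45 minutes.
- With 0.5 hours restored: 0.5 − 0.25 = 0.25 hours = 15 minutes, then 1 − 0.5 = 0.5 hours = 30 minutes. The longest gap is 30 minutes.
- Scheduled readings in the first hour: 2 as written (0.25 and 1), 3 as evidently intended (0.25, 0.5 and 1).
- The 0.5-hour PK sample becomes the only one in the first 2 hours with no matching supine reading.

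**4. Whether the orthostatic series closes the gap**

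It includes a supine measurement (Section 7.2.3), but its first postdose time is 1 hour, so nothing in it falls between 0.25 and 1 hour.

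**5. Largest possible extent**

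8 groups × 8 subjects × 1 reading = 64 readings, of which 8 × 6 = 48 are on L606 and 8 × 2 = 16 on placebo. This is a ceiling. It assumes that the footnote is followed literally in every group.

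**The case against.** The strongest reply is that the slip corrects itself. Nobody is likely to read a sequence of 0.25, 30, 1 as fifteen minutes, thirty hours, one hour. The right value stands in footnote m of the same table, and staff will be with the subject for the 0.5-hour PK draw in any case. Data are reviewed after every group, so a missing time point would probably be seen early.

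The consequence is also limited under a literal reading. The supine stopping rule concerns symptomatic falls, and Section 7.2.3 allows extra measurements when clinically appropriate, so a subject with symptoms would be measured whatever the list says. Scheduled readings at 0.25, 1, 1.5 and 2 hours remain. Holter recording covers heart rate throughout the gap, although not blood pressure. Section 8.4 plans no formal safety analysis.

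Most of this stands. It removes most of the link to the stopping rule and makes 64 lost readings an upper limit that is unlikely to be reached. It does not make the text right. The footnote is the operative schedule for a primary safety measure, and no other text overrides it. What would be lost is the routine half-hour reading in subjects without symptoms, where an unreported fall in pressure would otherwise be recorded. That time point would also drop out of the descriptive summaries of change from baseline.

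The protocol nowhere states 0.5 hours for vital signs. That value is inferred from the order of the list and from footnote m.

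**Conclusion.** The point holds: footnote h is wrong as written. Read literally, one of nine postdose supine readings moves to 30 hours, the first hour has two scheduled readings instead of three, and its longest gap is 45 minutes instead of 30. This would affect up to about 64 subjects, one reading each. The result is conditional on sites or database builders following the text; a careful reader would probably notice. No sample size, estimate or test depends on it. The intended value of 0.5 hours is an inference, but a strong one: it is the only simple reading that restores the order of the list, and it matches the PK list at the same position.

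**What to change.** In footnote h to Table 3 (Appendix 5), confirm the intended time and replace 30 with 0.5. The postdose supine times then read 0.25, 0.5, 1, 1.5, 2, 4, 8, 12 and 24 hours. Check that the case report form and site worksheets carry the same times. No other vital-sign or PK time changes. The cost is one entry in one footnote, with no added reading, blood sample, visit or equipment.

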## **1.2.4.** Pharmacokinetic Profile of Inhaled Treprostinil

Two studies characterized the pharmacokinetic (PK) profile of single doses of inhaled treprostinil in healthy volunteers. Eighteen subjects were enrolled in a 3 period crossover bioavailability (BA) study. The absolute BAs of the inhaled treprostinil 18 and 36  $\mu$ g were compared to a 15-ng/kg/minute (60 minute) IV infusion of treprostinil. Forty subjects were enrolled in a maximum tolerated dose (MTD) study of 54, 72, 78, 84, and 90  $\mu$ g of inhaled treprostinil. Maximum observed plasma concentration (Cmax), time of the maximum observed plasma concentration-time curve (AUC) from time zero to infinity (AUC0-∞) were determined in both studies.

In the bioavailability (BA) study,  $C_{max}$  and  $AUC_{0-\infty}$  were dose proportional following a single administration of inhaled treprostinil 18 or 36 µg and resulted in 64% and 72% absolute systemic BA, respectively. The mean  $t_{max}$  was 0.15 hours for both inhaled doses.

In the MTD study, inhaled treprostinil was dose proportional for  $AUC_{0-\infty}$  (mean range: 0.661 to 1.579 ng\*hr/mL) and  $C_{max}$  (mean range: 790 to 1708 pg/mL). The mean  $t_{max}$  was 0.20 hours across all doses. Adverse events (AEs) of chest pain, chest discomfort, nausea, and vomiting in the 90 µg cohort were determined to be intolerable; thus the MTD for a single dose of inhaled treprostinil was 84 µg.

Protocol	CONFIDENTIAL
	Protocol Number: PBI L606_2.0

Inhaled treprostinil remained detectable in the plasma approximately 4 hours after inhalation in both studies. Apparent plasma terminal elimination half-life ( $t_{1/2}$ ), calculated using a noncompartmental model, ranged from 0.46 to 0.76 hours across both studies.

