Estimated AUC at Starting Dose	-	-	0.57 0.8 ng•h/mL / (43.2 μg/kg / 30.6 μg/kg)
Safety Margin to Respirable HED or AUC	6.3-fold (193.55 µg / 30.6 µg)	3.8-fold (193.55 µg / 51 µg)	~97-fold (55.4 ng•h/mL / 0.57 ng•h/mL)

 Table 1:
 Summary of Starting Dose Calculations

Abbreviations: AUC = area under the plasma concentration-time curve; HED = human equivalent dose; NOAEL = no observed adverse effect level.

A non-GLP 10-day inhalation toxicity study in rats showed L606 had reduced clinical incidence during inhalation exposure compared to Tyvaso, suggesting L606 may be better tolerated. Treprostinil  $C_{max}$  is considered related to patient adverse effects both locally and systemically. Encapsulation of treprostinil in liposome improved the PK profile in terms of reducing  $C_{max}$  and exerting a stable plasma level for an extended duration (up to 8 hours). In contrast, the Tyvaso exhibited an immediate release in lung and rapid adsorption, distribution, and metabolism in plasma, resulting in high peak-trough fluctuations during a treatment session of 4 hours. L606 formulation exhibited a preferential PK profile with a comparable  $C_{max}$  value at the target dose of 48 µg/kg to that of Tyvaso at the target dose of 6 µg/kg. These results suggest the MTD for L606 could be 8 times higher than the MTD for Tyvaso. The planned maximum L606 emitted dose is 480 µg, which is expected to yield a respirable dose that is less than 4 times the Tyvaso maximum tolerated respirable dose.

Details of all doses administered will be documented in the TMF.

Treprostinil Formulation	Reference/Cohort	Loaded Dose (µg)	Loaded Volume (µL)	Emitted Dose (µg)	Respirable Dose (µg)
Tyvaso	Initial Dose			18	14.4
	Recommended Dose			54	43.2
	Maximum Tolerated Dose			84	67.2
L606 a	Cohort 1	60	40	51	30.6
	Cohort 2	120	80	102	61.2
	Cohort 3	180	120	153	91.8
	Cohort 4	240	160	204	122.4
	Cohort 5	300	200	255	153.0
	Cohort 6	360	240	306	183.6
	Cohort 7	420	280	357	214.2
	Cohort 8	480	320	408	244.8

 Table 2:
 Tyvaso Reference Doses and Planned L606 Doses

Tyvaso emitted dose  $\times 80\%$  = respirable dose (80% is the fine particle fraction of the Tyvaso inhalation system) L606 loaded dose  $\times 85\%$  = emitted dose (85% is the emission efficiency of the L606 nebulizer) L606 emitted dose  $\times 60\%$  = respirable dose (60% is the fine particle fraction of the L606 nebulizer)

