### 5.2. Study Treatment Administration

Each dose of L606 and placebo solution will be self-administered by the subject via oral inhalation. The entire treatment procedure will be completed within 10 minutes.

Subjects will be administered the IMP in numerical order while seated and may be semi-recumbent but will not be permitted to lie supine for 2 hours after dosing, except as necessitated by the occurrence of an AE(s) and/or study procedures.

The planned emitted dose escalation groups are:

- Cohort 1: 51 µg L606 or placebo volume equivalent to 51 µg
- Cohort 2: 102 μg L606 or placebo volume equivalent to 102 μg
- Cohort 3: 153 µg L606 or placebo volume equivalent to 153 µg
- Cohort 4: 204 µg L606 or placebo volume equivalent to 204 µg
- Cohort 5: 255 µg L606 or placebo volume equivalent to 255 µg
- Cohort 6: 306 µg L606 or placebo volume equivalent to 306 µg
- Cohort 7: 357  $\mu$ g L606 or placebo volume equivalent to 357  $\mu$ g
- Cohort 8: 408 µg L606 or placebo volume equivalent to 408 µg

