### 7.1. Pharmacokinetic Assessments

## 7.1.1. Sample Collection and Processing

Blood samples (approximately  $1 \times 4$  mL) will be collected by venipuncture or cannulation at the times indicated in the Schedule of Assessments in Appendix 5. Furthermore, up to 3 additional blood samples may be taken from each subject per treatment period, with the maximum volume of blood withdrawn per subject not exceeding the limit detailed in Appendix 3. Any changes to the scheduled times of PK assessments will be agreed with the Sponsor and documented in the TMF. Samples taken from subjects who received placebo will not be analyzed.

Procedures for collection, processing, and shipping of PK blood samples will be detailed in a separate document.

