### 8.3. Pharmacokinetic Analyses

Noncompartmental PK analysis will be performed on individual plasma concentration data, using commercial software such as Phoenix® WinNonlin®. Plasma concentrations of treprostinil and PK parameters will be listed and summarized using descriptive statistics (arithmetic mean, standard deviation, minimum, median, and maximum, geometric mean, and geometric coefficient of variation, as appropriate). Individual and mean treprostinil concentration-time profiles will also be presented graphically.

The AUCs and  $C_{max}$  will be the primary endpoints for the evaluation of dose proportionality. Dose proportionality of treprostinil will be evaluated by assessing the slope from regression analysis of log(AUC or  $C_{max}$ ) versus log(dose) from the power model for those subjects who receive L606.

Further details of the statistical analysis of the data will be addressed in the Statistical Analysis Plan.

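### The first PK sample comes 0.25 h after the end of inhalation, later than the tmax cited for inhaled treprostinil, so the peak of any rapidly absorbed fraction may be under-recorded

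*Protocol*

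**What the plan says.** Appendix 5, footnote m, sets PK sampling at "Day 1 predose and at 0.25, 0.5, 1, 1.5, 2, 4, 6, 8, 10, 12, 14, 16, and 24 hours postdose", and states: "Sampling times postdose are relative to the end of the inhalation treatment". Section 5.2 limits the inhalation: "The entire treatment procedure will be completed within 10 minutes". No sample is fixed during inhalation, at its end, or in the 15 minutes after it.

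For inhaled treprostinil solution, Section 1.2.4 reports a mean tmax that "was 0.15 hours for both inhaled doses" in the bioavailability study and "was 0.20 hours across all doses" in the maximum tolerated dose study, with a half-life of 0.46 to 0.76 h. It does not say whether tmax was counted from the start or the end of inhalation.

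Cmax and AUC0-2hr are endpoints (Section 2.2.2). The AUCs and Cmax "will be the primary endpoints for the evaluation of dose proportionality" (Section 8.3). Section 3.5 says that treprostinil Cmax "is considered related to patient adverse effects both locally and systemically". Section 7.1.1 provides that "up to 3 additional blood samples may be taken from each subject per treatment period" but does not tie these samples to any time.

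**The concern.** The schedule is thinnest where a fast component would show. L606 is expected to release slowly, but this is its first use in humans. The sustained-release evidence in Section 1.3 comes from intratracheal dosing in rats, a route chosen to reduce the effects of aerosol size and device. It therefore does not test what a mesh nebuliser does to the liposomes. If some treprostinil reaches the lung unencapsulated, it should behave like the solution and peak before the first sample.

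Cmax would then be under-recorded, and Cmax is the quantity the protocol links to adverse effects. Counting from the end of inhalation also leaves exposure during inhalation out of the AUC and moves the 0-2 h window later. Loaded volume rises from 40 to 320 µL across cohorts (Table 2). If inhalation time rises with volume, the error would differ by dose within the dose-proportionality regression.

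**Working it through.** **The plan's own figure.** Appendix 3 allows 17 PK samples and 68 mL. Footnote m gives 1 predose and 13 postdose samples, and Section 7.1.1 adds 3 optional ones: 1 + 13 + 3 = 17, and 17 × 4 mL = 68 mL. With the other rows, 48 + 3.5 + 68 = 119.5 mL. The figures reproduce, and the optional samples are already counted.

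**Timing.** From the end of inhalation the first sample is at 0.25 h. From the start of a 10-minute inhalation it is at 0.25 + 10/60 = 0.417 h. Both are later than 0.15 and 0.20 h.

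**Check A: how much of a solution-type peak remains at the first sample.** Share = 2^(−(t_first − tmax)/t½), with t½ of 0.46 or 0.76 h.

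- tmax counted from the end: lowest 2^(−0.10/0.46) = 0.86, highest 2^(−0.05/0.76) = 0.95.
- tmax counted from the start, 10-minute inhalation: lowest 2^(−0.267/0.46) = 0.67, highest 2^(−0.217/0.76) = 0.82.

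So 67-95% of the peak is still present. It is blunted, not lost.

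**Check B: a model for L606.** The half-lives and sampling times come from the protocol. The rest is assumed: one compartment, even deposition over T = 3 or 10 minutes, free fraction f absorbed at 20/h, and the remainder released with a 3 h half-life (ln 2/3 = 0.231/h). With ke = ln 2/t½ (1.507 or 0.912/h), a pathway with rate k has step response

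g(t) = (1/T)·[(1 − e^(−ke·t))/ke − (e^(−ke·t) − e^(−k·t))/(k − ke)],

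and concentration g(t) − g(t − T). Observed Cmax is the largest value at the scheduled times. AUC0-2hr is the linear trapezoid from the end of inhalation with zero at time zero, divided by the true exposure in the first 2 h from the start.

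| Free fraction | Observed Cmax low by |
|---|---|
| 10% or less | under 1% |
| 25% | 0.5-7% |
| 50% | 4-13% |
| 100% | 6-17% |

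The AUC0-2hr ratio runs from 0.80 (100% free, 10 minutes, t½ 0.46 h) to 1.09 (no free drug, 10 minutes, t½ 0.76 h). AUC0-24hr is 99-100% of true at 10% free and 96-99% at 25%.

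**Sensitivity to absorption rate.** With absorption instead tuned to the cited tmax for inhalations of 2 to 8 minutes, and an assumed rate at 10 minutes, observed Cmax is 99.6-100% of true at 10% free, 85-100% at 25%, 76-98% at 50% and 71-97% at 100%.

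**Dose proportionality.** Assume inhalation time grows with volume from 1.25 to 10 minutes. Under the model of check B, the Cmax power-model slope falls below the slope for true Cmax by at most about 0.016 at 25% free and about 0.035 at 100%.

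**With added samples at 0 and 5 minutes after the end.** Under the model of check B, observed Cmax is at least 95% of true in every case. AUC0-2hr, on actual times from the start, comes within about 3% of true.

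**The case against.** The cited tmax belongs to an immediate-release solution, and its time origin is not given. If it was counted from the end of inhalation, the first sample is only 3 to 6 minutes late. The protocol gives no free fraction and describes high loading efficiency, slow release and a stable level for up to 8 hours. Five samples in the first 2 hours would show a large burst. All of this stands, and it is why the size of the effect can only be given as a range over assumed free fractions.

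A reader might infer that the burst would be missed, that the schedule favours the product, or that it weakens the escalation check. The documents support none of these:

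- Most of an immediate-release peak is still visible at 0.25 h.
- The AUC0-2hr error runs in both directions. With no free drug it is overstated by 1-9%.
- The trial has no Tyvaso arm.
- Section 3.7 contains no Cmax or AUC limit, and Section 3.1 has PK reviewed as available. There is no numeric PK rule for a few percent to upset.

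Two further points limit the case. Section 7.1.1 already permits extra samples and agreed changes to sampling times. Actual-time handling in the noncompartmental analysis is commonly left to the SAP, so its absence here is no finding. However, a SAP cannot recover samples never drawn, and samples added after an early cohort would leave cohorts on different schedules.

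The remedy is also not uniformly effective. With a 3-minute inhalation, 25% free and a half-life of 0.46 h, observed Cmax is 95.5% of true with or without the two samples.

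**Conclusion.** The point holds as a cheap improvement, not as an error or contradiction. The first sample falls after the protocol's own tmax for inhaled treprostinil solution, so the peak of any rapidly absorbed fraction may be under-recorded. Under the stated model the Cmax loss is negligible at 10% free or less, a few percent at 25%, and at most about 17% with no liposomal retention at all. Absorption tuned to the cited tmax gives larger losses, up to 29% in that same extreme.

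The finding that later AUCs change little holds for free fractions of 25% or less. If nearly all the drug were free there would be no later phase, and the early loss would carry into them. The effect on the dose-proportionality slope is small. All these sizes rest on an unstated free fraction and on assumed release, absorption and inhalation times. The sampling gap itself does not.

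**What to change.** In footnote m, assign two of the three optional samples to the end of inhalation and about 5 minutes later, in every cohort from the first. Record the start and end of each inhalation. Add one sentence saying that AUC and tmax are calculated on actual times from the start of inhalation.

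Blood volume does not change: the two samples take 2 × 4 = 8 mL of the 68 mL already allowed in Appendix 3. The cost is one optional sample in reserve instead of three, and a busier first 15 minutes, with two extra draws shortly before the 0.25 h vital signs, which need 5 minutes supine beforehand (Section 7.2.3).
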